Management Among Adults with Hypertension

- 4.2.** The inclusion criteria will be: adults from 18 to 75 years old, ability to self-consent, English-speaking, able to read/write English, currently prescribed at least one medication for treatment of essential primary hypertension.
- 4.3.** There will be no special populations in this study. This study will not include adults unable to consent; individuals who are not yet adults (infants, children, teenagers); pregnant women; or prisoners.
- 4.4.** Pregnant women will be excluded due to the complexity of hypertension in pregnancy, which warrants management by an OB/GYN or other specialists. Potential participants will be asked if they are pregnant or planning to become pregnant using the screening document “UNM HTN phone screen for potential patients.” Children are excluded for three reasons: 1) the writer is only certified as an NP to work with adults; 2) the focus of this study is the population at greatest risk for high blood pressure which is adults; and 3) children with high blood pressure are rarely diagnosed with essential primary hypertension, and should be managed by a specialist. We do not have the resources to provide adequate materials in Spanish or other languages commonly spoken in NM, and further research may be needed on the effect of the intervention for non-English speaking patients.

5. Number of Subjects

- 5.1.** This is a single site study and will be done at one location, Walgreens Store #6587 in Albuquerque, New Mexico. There will be 50 participants recruited.
- 5.2.** The number to be recruited will be 50.
- 5.3.** Based on statistical analysis from UNM Statistics Department, a sample size of at least 45 patients is needed. The number to be recruited at the onset will be 50 to account for attrition.

6. Study Timelines

- 6.1.**
 - Duration of individual’s participation in research: The total expected duration of participants’ active participation is less than 60 minutes. The participants will have mailed to them at the start of the study: one-page with supplemental handouts/visual aids, list of suggested apps and web sites, pre/post survey and pre/post-test with self-addressed stamped envelopes (SASE) to return their information, and a pill box.
 - Recruitment for this study will begin August-September 2020. Duration anticipated to enroll all subjects: 30 days

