 - Total duration for researchers to complete the study: Recruitment will occur through end of Sept 2020; additional follow-up phone calls will occur through

PROTOCOL TITLE: Evaluating the Effect of an Evidence-Based One Page with
Supplemental Visual Aids on the Knowledge and Perceptions of Blood Pressure
Management Among Adults with Hypertension

September-November 2020. Data analysis will occur during the month of December 2020. Manuscript preparation and submission to scholarly publications will occur shortly thereafter with the target of January 2021.

7. Study Endpoints

- 7.1.** Primary endpoint: change in participant's knowledge of blood pressure management; change in participant's perception of making lifestyle changes to manage their hypertension
- 7.2.** Describe any primary or secondary safety endpoints: N/A
- 7.3.** Describe any exploratory endpoints:
 - 1: Participants will be asked to rate the usefulness, ease of reading, and attractiveness/visual appeal of each handout they were provided.
 - 2: Participants who choose to use any apps or web sites will be asked for feedback on usefulness, ease of reading/access, and attractiveness/visual appeal for each app or web site used.
 - 3: The subset of participants who choose to use electronic resources will be compared to the subset of participants who do not to compare any differences in the primary outcome.

8. Research Setting

- 8.1.** Site or location: Walgreens Store #6587 in Albuquerque, NM.
- 8.2.** We will recruit potential subjects from Walgreens Store #6587 in Albuquerque, NM. Participants will be recruited over the phone.
- 8.3.** Research will be performed from Walgreens Store #6587 in Albuquerque, NM.
- 8.4.** Describe the composition and involvement of any community advisory board: N/A
- 8.5.** This is a partnership with UNM College of Pharmacy, Walgreens Pharmacy, and a Doctor of Nursing (DNP) student enrolled in the DNP program at Missouri State University (MSU). Per MSU policy, once the IRB is submitted and approved through UNM, the IRB approval from UNM with a summary paragraph will be submitted to MSU for record. [name], DNP candidate, will be responsible for submitting the approved UNM IRB with summary paragraph to the MSU IRB board to complete this requirement. A cede letter is included in this submission.

9. Resources Available

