12.2 Patients will be screened for eligibility for the study at Walgreens Store #6587, with pharmacists supervising the PharmD students. Screening will be conducted with the Interview Guide included in this IRB submission as "UNM HTN Prescreen for Potential Participants." Eligible potential participants will have consent forms read and given the opportunity to ask questions about the study. Participants may choose to enroll in the study at that time, or given more time to be mailed consent forms at home and decide at another time. Once the participant consents to participation, the materials will be mailed to the participant, and the participant will complete a pre-survey ("Pre-survey for UNM HTN Study") and pre-test ("Pre-test for UNM HTN Study") on blood pressure management. Participants will be provided a one-page education with supplemental visual aids on blood pressure management with education provided by PharmD students ("My Planned Behavior for Managing My Blood Pressure"). Participants will be provided a list of suggested apps and websites ("Evidence-

PROTOCOL TITLE: Evaluating the Effect of an Evidence-Based One Page with
Supplemental Visual Aids on the Knowledge and Perceptions of Blood Pressure
Management Among Adults with Hypertension

based Websites and Apps for Blood Pressure Management") that they may use if they have a smartphone and/or internet access.

After an initial teaching phone call performed by a PharmD student, a follow-up phone call will be conducted at week 4 and 8 of the participant's enrollment.

During each phone call, study personnel will use a telephone script titled "Phone Call Script for My Planned Behavior for Managing My Blood Pressure Participants" to discuss blood pressure goals, behavioral changes, and principles of blood pressure management.

At week 8, participants will either answer their questions over the phone or be reminded to complete a post-test ("Post-test for UNM HTN Study") and post-survey ("Post-survey for UNM HTN Study") and mail in using their SASE.

12.3 The information will be collected prospectively and information will be collected at the onset of enrollment, during an initial teaching phone call, during phone calls at week 4, and 8, and from mailed in pre/post-test; pre/post surveys.

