- Post-survey ("Post-survey for UNM HTN Study"): Walgreens Store #6587. The purpose of this survey is to gauge the participant's perspectives on engaging in behavioral changes after the educational intervention. The patient may return the completed test by mail, or answer the questions over the phone if they are unable to mail their responses.

13 Data Analysis

- 13.1 Descriptive statistics will be used with demographic information, and paired t-tests will be used for the pre/posttest and pre/post surveys. The UNM Statistics Department will assist with statistical analysis.
- 13.2 Power analysis completed for the paired t-tests to detect difference in pre/post tests and surveys using: one tail, moderate effect size of 0.5, alpha probability of error of 0.05, and power standard of .95 resulted in n=45 (GPower, 2019).

14 Provisions to Monitor the Data to Ensure the Safety of Subjects

N/A. This study poses minimal risk to the patient as it utilizes only non-invasive screening interventions (education; surveys; follow-up phone calls).

15 Withdrawal of Subjects

- 15.1 A patient may be withdrawn from the study should they no longer meet inclusion criteria (for example, if they become pregnant during the study). The patient may also be withdrawn if they are not following the study protocol as agreed upon at the onset of the study. Should the patient no longer be able to be contacted after three phone call attempts, they will be withdrawn from the study. Data obtained up to that point of no contact will be maintained, and used for the study analysis.
- 15.2 The completion of this study will be on the final call to gather data & final post-test and post-survey from the participant. If the patient did make a behavior change of taking blood pressure at home, we will inquire at this time. Upon completion of the study, the participant will be encouraged to continue to see their primary care physician or other medical provider for continued blood pressure management.

PROTOCOL TITLE: Evaluating the Effect of an Evidence-Based One Page with
Supplemental Visual Aids on the Knowledge and Perceptions of Blood Pressure
Management Among Adults with Hypertension

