15.3 This is an education-only intervention, and the patient may choose to immediately withdraw from the study and decline any further education or follow up phone calls. Should the patient choose to withdraw at any time, they will be encouraged to follow-up with their primary care physician or other medical provider for continued blood pressure management. Should the patient no longer be able to be contacted after three phone call attempts, they will be withdrawn from the study. Data obtained up to that point of no contact will be maintained, and used for the study analysis. Should there be unexpected circumstances such as pregnancy or hospitalization for a major cardiac event (stroke, myocardial infarction, or heart failure exacerbation), that participant's data will be used up to the time of the event that causes withdraw.

15.4 Collected data for any withdrawn participants will be maintained in accordance with study protocol.

15.5 Participants will be informed in the consent process that they may choose to withdraw from the study at any time for any reason.

16 Data Management/Confidentiality

16.1 N/A Data will be entered and stored on UNM Redcap.

16.2 The research team will have access to stored information about the subjects that will be maintained in a locked filing cabinet inside a pharmacy that is accessible only with keys and/or personal access codes. The research team will have access to the UNM Redcap Database.

16.3 This research will involve the collection of patient's name. The patient's name is needed for review of their medication profile at Walgreens and for making follow-up phone calls. Participants will be assigned an ID code to be placed on all documents. The ID code and the participant's name will not be recorded on the same documents. The only link between ID code and participants' names will be on a master list which will be stored in a locked filing cabinet which will be placed inside a pharmacy accessible only via personal access codes and keys. Information contained on envelopes that patients may mail back to the pharmacy (patient name and address) will be shredded upon receipt.

16.4 This research will involve access to Protected Health Information (PHI), including the patient's medication profile at Walgreens.

16.5 The data is not publicly available.

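### Sections 15.1 and 15.3 let missed calls close off post scores that could still arrive by mail, and the paired t-tests in 13.1 then omit those participants

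*Combined protocol and SAP*

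**What the plan says.** **Withdrawal.** Section 15.1, and again 15.3: "Should the patient no longer be able to be contacted after three phone call attempts, they will be withdrawn from the study". Both continue: "Data obtained up to that point of no contact will be maintained, and used for the study analysis". Section 15.1 adds a second ground: "The patient may also be withdrawn if they are not following the study protocol as agreed upon at the onset of the study". For pregnancy or a major cardiac event, 15.3 says the participant's "data will be used up to the time of the event that causes withdraw".

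**How the post scores are collected.** Under 6.1 the post-test, post-survey and return envelopes go out in the first mailing. Sections 12.2 and 12.5 allow return by mail, or answers by phone. The prompt is the last call: "At week 8, participants will either answer their questions over the phone or be reminded to complete a post-test" (12.2). Section 15.2 also ties the end of the study to that call: "The completion of this study will be on the final call to gather data". Section 12.4 names mail-outs as a way of gathering the remaining information, and 21.2 names mailed-in information as a follow-up route. Neither describes a reminder.

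**Consent.** Section 25.1.5 asks for renewed verbal consent at each call and stops data collection for anyone who does not give it.

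**Analysis.** The primary endpoints in 7.1 are change in knowledge and change in perception. For these, 13.1 names paired t-tests and nothing else. Section 5.3 deals with loss only by recruiting more: "The number to be recruited at the onset will be 50 to account for attrition", against 45 needed. On timing, 6.1 says: "Data analysis will occur during the month of December 2020". The text gives no analysis set, no rule for a missing score and no cut-off date for forms.

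**The concern.** The withdrawal rule turns on phone contact, but the outcome does not depend on it. Someone who stops answering still holds the forms and the envelope. If withdrawal closes data collection, the study gives up primary-endpoint scores that one reminder might recover. Those given up are not a random subset: they are people who missed calls or were judged not to be following the protocol, in a trial whose intervention is education and calls.

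A paired t-test needs both scores, so a participant with only a pre score adds nothing to either primary endpoint. No comparison group is described, so the mean change among those who returned both forms is the whole result. If the people lost changed by a different amount, that mean does not describe the enrolled group, and the plan gives the reader nothing with which to judge the gap.

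**Working it through.** **1. The plan's own figures.** Inputs from 13.2: one-sided alpha 0.05, standardised effect 0.5, power 0.95. For a paired t-test with n pairs, power comes from the noncentral t distribution with n − 1 degrees of freedom and noncentrality 0.5 × √n. At n = 45 the noncentrality is 3.354 and power is 0.951; 45 is the smallest n that reaches 0.95. The plan's 45 is reproduced. Recruiting 50 for 45 implies a loss of 5/50 = 10%, since 45/(1 − 0.10) = 50. The documents do not state that rate.

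**2. Shift from leaving out those lost.** Let L of 50 have no post score, completers gain c, and those lost gain g, in SDs of the change score.

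All-enrolled mean = [(50 − L)c + Lg]/50, so completer mean − all-enrolled mean = L(c − g)/50.

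Assumed: c = 0.5 (the 13.2 effect size), with g varied. Loss above 5 is also assumed.

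| Lost of 50 | g = 0 | g = 0.25 | g = 0.5 | g = 0.75 | Power, n = 50 − L |
|---|---|---|---|---|---|
| 5 | +0.05 | +0.025 | 0 | −0.025 | 0.951 |
| 10 | +0.10 | +0.05 | 0 | −0.05 | 0.928 |
| 15 | +0.15 | +0.075 | 0 | −0.075 | 0.895 |
| 20 | +0.20 | +0.10 | 0 | −0.10 | 0.848 |

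At 5 lost, the 95% half-width of the completer mean is 0.30 SD, so a shift of 0.05 is one sixth of it (0.05/0.30). Power falls slowly with loss; the shift grows in proportion to it.

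**3. Loss related to the pre score.** Simulation with pre/post correlation 0.5, true gain 0.50 and a logistic chance of loss with slope 1 per SD of pre score (all assumed). When higher scorers are lost more, completers show 0.546 at 10% lost and 0.588 at 20%. When lower scorers are lost more, they show 0.455 and 0.413. A likelihood-based model using every pre score stays at 0.50 (0.497 to 0.501). When loss is unrelated to the pre score and those lost gain 0, the same model still gives about 0.50 while the all-enrolled mean is 0.45 at 5 lost and 0.30 at 20 lost. It corrects the first kind of loss and not the second.

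**4. No-change figure.** If non-returners are taken as unchanged, the mean is c × (50 − L)/50. With c = 0.5 this is 0.45, 0.40, 0.35 and 0.30 for 5, 10, 15 and 20 lost. An interval around it misleads either way. Filling in zeros gives 95% half-widths of 0.27, 0.26, 0.25 and 0.23, which shrink as more people are lost. Multiple imputation with the change shifted down by the completers' estimated mean gives, at 20 lost, a standard error of 0.19 by Rubin's rules against an actual 0.11. The figure is best reported without an interval.

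**5. Calendar.** Enrolment runs to the end of September 2020 (6.1). Enrolment on 30 September plus 56 days is 25 November 2020. A cut-off of 30 November would leave that person five days.

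**The case against.** The strongest reply is that this is small. The only loss the documents imply is 5 of 50. There, even if those lost gained nothing, the shift is 0.05 SD and power is 0.951. Every larger figure rests on a loss that no section predicts. That stands; it makes this a correction to a rule, not a threat to the trial.

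Four stronger readings are tempting, and the documents support none of them.

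- A reader might infer that the reported gain will be too large. Nothing shows how those lost would have changed. If they gained as much as completers there is no bias, and if they gained more the result is too small.
- A reader might infer that late forms are barred. Sections 15.1 and 15.3 say that data up to loss of contact are used; they do not say that later forms are refused. Section 12.3 lists mailed forms as a data source without requiring phone contact, and 25.1.5 stops collection only for someone who does not consent to continue. The point is that the rule can be applied so as to exclude them, and nothing settles it.
- A reader might infer a broken promise to use withdrawn participants' data. The promise concerns the study analysis in general, and descriptive statistics could meet it. It simply does nothing for the two change endpoints when only a pre score exists.
- A reader might infer that people who miss calls can never be prompted. Sections 12.4 and 21.2 name mail as a follow-up route, and the phone script and consent document were not available to check. What can be said is that no mailed reminder is described.

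It is also fair to say that the all-enrolled mean is a yardstick chosen here. Hypothesis 1.2 concerns patients after the teaching, so someone lost before the teaching call is arguably outside it. That limits how the shift should be read, but it gives no reason to lose scores from people who were taught and later missed calls.

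**Conclusion.** The point holds as a defect in a stated rule. Sections 15.1 and 15.3 tie withdrawal to missed calls or non-adherence, although the post scores can arrive without a call. Applied as written, the rule can discard obtainable scores, and 13.1 then leaves those participants out of both primary endpoints.

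The direction of any bias cannot be known from the documents. Its size is 0.05 SD at 5 lost, 0.10 SD at 10 lost and 0.20 SD at 20 lost, assuming completers gain 0.5 SD and those lost gain nothing; smaller differences between the groups give smaller shifts. At the implied loss this is minor. It deserves correction because the remedy is cheap, and because a decision on late forms would otherwise be made after they arrive. The sample size of 45 is not in dispute. The five extra recruits protect power, but they do not protect against selective loss.

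**What to change.** **Sections 15.1 and 15.3.** State that missed calls, or not following the protocol, end the calls but not collection of the post-test and post-survey. Send one mailed reminder; 12.4 already names mail-outs, 16.11 shows that addresses are held, and the ID code in 16.3 lets a late form be paired. Accept forms from anyone who has not withdrawn or declined consent, up to one fixed cut-off date before the December 2020 analysis. Choose that date knowing that the last enrolled reach week 8 on 25 November. Reconcile this with 25.1.5 by saying that a form mailed by someone who has not declined may be used. State also whether forms are sought after the pregnancy and cardiac-event withdrawals in 15.3.

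**Section 13.1.** Keep the paired t-test as the primary analysis, on all participants with both scores, regardless of later call contact or adherence. Report the number of non-returners, their withdrawal reasons and their baseline scores. For each primary endpoint, add the mean change if non-returners are assumed unchanged (completer mean times the fraction returned), as a descriptive sensitivity figure without a confidence interval. A likelihood-based repeated-measures model using all pre scores may be added, with a statement that it corrects only loss related to the pre score. Multiple imputation is not recommended here, for the reason in step 4 of the working.

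**Cost.** IRB review of the wording, one mailing and a little more analysis. The reported gain may be smaller.

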16.9 N/A

16.10 Data will not be transferred or transmitted to outside locations or entities. Data will be stored in locked filing cabinet inside a pharmacy that is only accessible with keys and/or personal access codes. Data will be entered into UNM Redcap. No data will be sent to MSU, other than in final summary form. Information contained on envelopes that patients may mail back to the pharmacy (patient name and address) will be shredded upon receipt.

16.11 Collected information will include answers to initial screening questionnaire, patient name, date of birth, gender, ethnicity, phone number, mailing address, pre/post-tests, pre/post-surveys, self-reported blood pressure readings, and self-reported medication changes. Data collected on hard copy forms will be input into UNM RedCap. Data will be recorded onto a hard copy forms for initial screenings, pre/post-tests, pre/post surveys, consent/HIPAA forms. Data will be stored for 6 years after initial consent. Only study personnel will have access to data.

16.12 N/A

16.13 N/A-Data will not include audio or video recordings

16.14 N/A-Data will not include photographs

16.15 Research records will be maintained for 6 years after initial consent and HIPAA authorization.

16.16 N/A – minors are not included in this study

16.17 HIPAA Requirements: Records will be retained for 6 years after each subject's initial consent.

17 Data and Specimen Banking

Data collected in this study will only be used for the completion of this project and not used in any future projects.

No specimens will be collected/banked in this study.

18 Risks to Subjects

18.1 This study poses minimal risk to the participants, and uses only non-invasive interventions. The intervention consists of education intended to assist the patient with behavioral changes that may result in improved blood pressure management. Participants may experience some discomfort when answering pre-test/survey or post-test/survey questions. Participants may experience a loss of confidentiality

PROTOCOL TITLE: Evaluating the Effect of an Evidence-Based One Page with Supplemental Visual Aids on the Knowledge and Perceptions of Blood Pressure Management Among Adults with Hypertension

and/or privacy.

19 Potential Benefits to Subjects

19.1 The potential benefit for the participant is to achieve a better understanding of positive behavior changes to continue management of their blood pressure after study ends.

20 Recruitment Methods

20.1 Participants will be recruited from Walgreens Store #6587 by phone call. Participants will be recruited through the end of September 2020.

20.2 Potential participants are those who pick up their medications from the pharmacy, and during standard-of-care follow-up phone calls from Walgreens Pharmacy. The participants' medication profile will be reviewed and an initial interview will be conducted to determine if they meet study criteria.

21 Provisions to Protect the Privacy Interests of Subjects

21.1 Recruitment: Participants will be screened for interest by phone call during a standard-of-care follow-up phone call from Walgreens Pharmacy. The person making the phone call to collect the data will be in a secure area with no other/outside people able to hear the conversation. The person making the call will ask the participant at the onset of the call if this is a good time for them to talk so the receiver of the call also has their own privacy.

21.2 All follow up will be conducted by phone calls or mail-in information. The person making the phone call to collect the data will be in a secure area with no other/outside people able to hear the conversation. The person making the call will ask the participant at the onset of the call if this is a good time for them to talk so the receiver of the call also has their own privacy.

22 Economic Burden to Subjects

22.1 There are no costs associated to the participant in this study.

23 Compensation

23.1 There is no compensation for participants. There will be an incentive of one complimentary pill box, valued at approximately \$5, for each participant.

24 Compensation for Research-Related Injury

24.1 There is no foreseeable injury as this study utilizes only non-invasive procedures and interventions.

25 Consent Process

PROTOCOL TITLE: Evaluating the Effect of an Evidence-Based One Page with
Supplemental Visual Aids on the Knowledge and Perceptions of Blood Pressure
Management Among Adults with Hypertension

25.1 Participants will be verbally consented prior to participating in the study.

25.1.1 Consent will be obtained by [name] and the PharmD students ([name], [name], [name], [name]) at the onset of the project verbally with each participant using the attached consent document generated from HRPO template version December 2, 2019. Study personnel participating in recruitment and consenting have completed CITI training. The students will be trained on the consent process, to include provisions for ensuring patient privacy, verbally reviewing the consent form and answering the participant questions. They will be using the teach-back method to ensure participant understanding.

25.1.2 The verbal consent process will take place over the phone from a private area at Walgreens Pharmacy.

25.1.3 The only incentive offered to the patients in this study is one pill box, valued at approximately \$5. No additional offers of incentives will be made to induce participation.

25.1.4 Participants will be verbally consented. Potential participants who wish to consider the consent for a longer may enroll at a later time during the enrollment period.

25.1.5 Participants will be asked to verbally consent to their continued participation in the study at each follow-up phone call and their final visit. If patient does not consent to their continued participation, their participation in the study will be ended and no further data collected.

25.1.6 Research personnel will verbally review the consent form with the participant to gauge the participant's understanding of the study procedures. Participants will have the opportunity to ask additional questions during the consent process.

25.1.7 The teach-back method will be utilized to ensure participant understanding of the consent (e.g. "We've talked about a lot of information today. If you were to tell a friend about this study, what would you tell them?")

Subjects not fluent in English – N/A; this study will only include English-speaking, reading, and writing individuals.

Cognitively Impaired Adults/Adults Unable to Consent/Use of a Legally Authorized Representative – N/A; this study will only include adults able to consent for themselves.

Subjects who are not yet adults (infants, children, teenagers) – N/A; this study will only include adults.

PROTOCOL TITLE: Evaluating the Effect of an Evidence-Based One Page with Supplemental Visual Aids on the Knowledge and Perceptions of Blood Pressure Management Among Adults with Hypertension

Waiver or Alteration of Consent Process (consent will not be obtained, required element of consent will not be included, or one or more required elements of consent will be altered) – We are requesting a waiver of obtaining a signature from subjects on a consent form to document consent. We are requesting to obtain verbal consent only, as this study will not be conducted face-to-face.

26. Documentation of Consent

26.1 Consent will be obtained using the script and consent document generated from HRPO template version December 2, 2019, included in this submission.

